#### 4. Background and Rationale:

Total laparoscopic pancreaticoduodenectomy (TLPD) remains one of the most advanced laparoscopic procedures. Owing to the evolution in laparoscopic technology and instrumentation within the past decade, laparoscopic pancreaticoduodenectomy is beginning to gain wider acceptance.(1)

Gagner and Pomp were the first to describe the laparoscopic Whipple procedure in 1994. The long operative times and technical difficulties coupled with the need to develop advanced laparoscopic skills were valid reasons that supported the initial reluctance to pursue these sophisticated minimally invasive operations. Recently, laparoscopic pancreaticoduodenectomy has started to gain wider acceptance as surgeons become more comfortable with laparoscopic technology. As a result, TLPDs have been reported with an increased frequency from institutions internationally.(2-15)

In recent years, total laparoscopic pancreaticoduodenectomy (TLPD) has been introduced as a feasible alternative to open pancreaticoduodenectomy (OPD) when performed by experienced surgeons in laparoscopic and pancreatic surgery. Its application has been gradually increased, but its safety, reproducibility, and oncological outcomes are still debated due to its technical complexity and prolonged operating time. There are different experiences present in the literature regarding indications, surgical techniques, postoperative outcomes, benefits and limitations of this approach, oncological results, learning curve, and costs. There is no standardized surgical technique for TLPD. Different techniques exist for both the demolitive stage and the reconstructive stage. We summarized the different aspects of the surgical technique based on the various experiences reported by different authors. Compared to OPD, TLPD provides the advantages of laparoscopy, i.e., reduced blood loss, decreased postoperative pain, and shorter length of hospital stay, without increasing the rate of postoperative complications or compromising oncological outcomes. With increased experience, more challenging cases may also be approached with this technique, including those requiring major vascular resections or multi-visceral resections.(16)

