Pancreaticoduodenectomy (PD) has seen improved perioperative outcomes and complication rates over the last few decades (17-20). Nevertheless, it continues to be a morbid operation with complications ranging from 24-59% (21-23). Laparoscopic surgery reduces surgical morbidity in various operations, however laparoscopic pancreaticoduodenectomy (LPD) is a relatively new procedure which lacks a clear consensus regarding its benefits (24-28). Although the first published case was described in 1994, it has been slow to gain popularity (29). This is likely in part due to the challenging technical aspect of the procedure including the retroperitoneal location of the pancreas, close vicinity to the superior mesenteric artery and vein, portal vein and hepatic arteries and the technical difficulty of three anastomosis. In recent years, however, we have seen an increasing

Cairo University

KASR ALAINY

CAIRO UNIVERSITY - FACULTY OF MEDICINE

number of studies examining LPD. Initial research evaluated feasibility and outcomes, assessing whether LPD could be done with adequate safety (30-37). The question then moved to compare to the open approach questioning if it will appreciate the same benefits of other laparoscopic surgeries. Partially enabled by higher volumes at specialized centers, studies began comparing LPD with (OPD). Although there are a handful of pancreaticoduodenectomy review articles evaluating LPD in the literature, many include papers with limited sample sizes and case reports. Our goal in this study is to compare and contrast the outcomes of both approaches aiming to reduce post operative morbidity and oncological outcomes.

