**- Methodology in details:**

- Patients will present to the outpatient clinic of KASR ALAINY hospitals with pancreatic head tumours, cholangiocarcinoma, duodenal tumours (1st, 2nd and 3rd part) and ampullary tumours who are fit for either open or laparoscopic pancreaticoduodenectomy.
- Full assessment will be done by clinical examination, radiological assessment in the form of EUS, CT scan and metastatic work-up, laboratory investigations in the form of tumour markers and tissue biopsy histopathological examination.
- Patients will be classified into frank resectable, borderline resectable (defined as pancreatic head masses larger than 4 cm in size, equivocal findings of ascites and metastases on CT scan and signs of advanced disease as in marked weight loss and markedly elevated CA19-9 > 1000) and frank irresectable.
- A decision will be made by the multidisciplinary team and patients will be selected to undergo total laparoscopic pancreaticoduodenectomy or open pancreaticoduodenectomy through a randomized manner
- Patients with tumours classified as borderline resectable tumours will be subjected to diagnostic laparoscopy prior to open surgery
- A diagnostic survey and intraoperative ultrasonography were performed to assess for resectability and other pathological conditions such as the presence of ascites, liver metastases and peritoneal deposits and a decision to proceed or abort will be made accordingly.
- Patients classified as borderline resectable will undergo an intraoperative ultrasound assessment of the vessel involvement, LNs and tumour size if irresectability is suspected.
- Open approach will entail a roof top incision
- Laparoscopic approach will entail trocar placement at the following sites:
  - 10 mm visual port at the level of the umbilicus
  - 12 mm port in the right mid-clavicular line 2 cm below the umbilicus
  - 5 mm port in the left mid-clavicular line 2 cm below the umbilicus
  - 5 mm port in the right mid-clavicular line 2 cm above the umbilicus
  - 5 mm port in the left mid-clavicular line 2 cm above the umbilicus
  - An optional 5mm port in the epigastric region if required
- Total internal stents will be placed inside the pancreatic and biliary anastomoses. The size of the stents will be determined according to caliber of pancreatic duct and common bile duct.
- Operative time will be calculated in minutes starting from skin incision to skin closure

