- Blood loss will be assessed in coordination with the anaesthesia team by counting the number of soaked towels and gauze and calculating the amount of blood suctioned throughout the procedure.
- Daily chest assessment to exclude or suspect lung atelectasis, pleural effusion or pneumonia will be done. Further chest imaging will be done if required.
- Daily serial abdominal examination to exclude or suspect pancreatic or biliary leakage will be done. Further laboratory assessment will be done if required (inflammatory markers: TLC, CRP, serum and drain amylase, serum and drain bilirubin), imaging in the form of an abdomen and pelvis CT study may be done if required.
- Daily wound assessment will be done starting 48 hours following surgery
- Pain assessment will be done by means of a visual analogue scale (VAS)
- Early patient satisfaction in terms of post-operative pain, early ambulation, ability to resume daily activities and complications by means of a questionnaire
- ICU stay and total hospital stay will be calculated
- Pathological assessment will be noted in terms of number of LNs harvested and the resection margins (R0 or R1)
- Incision / portsite examination to exclude incisional or portsite hernia.

○ **Does the research involve?**

Human participants

Biological samples/Tissues

Identifiable private data/Information

○ **Type of consent of study participants:**

Written consent

Oral consent

Cairo University

KASR ALAINY  
CAIRO UNIVERSITY - FACULTY OF MEDICINE

No consent needed (Please justify)

o **Potential risks:**

No attributed risks can be related to the study

o **Confidentiality of data:**

All study related information will be stored securely at the study site.

All participant information will be stored in locked file cabinets in areas with limited access.

Participants' study information will not be released outside the study without the written permission of the participant.

Research ethics committee "REC" & Health authorities have the right to review's patient's data

---

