**9- Study outcomes:**

- **Primary outcome:**

- o Operative time
- o Assessment of early post-operative complications including: pain, respiratory complications (collapse, pleural effusion or pneumonia)
- o Incidence of pancreatic and biliary leakage

- **Secondary outcome:**

- o ICU stay and total hospital stay
- o Patient satisfaction in terms of pain, ambulation, ability to resume daily routine activities
- o Blood loss and need for blood transfusion accordingly

- Wound complications including: infection (early) and incisional hernia/port site hernia (late)
- Pathological assessment in terms of LN harvesting and resection margins (R0 resection or R1)

---

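### The entry under Potential risks denies any study risk, but the protocol calls the safety of one randomised arm unsettled and measures harms as primary outcomes

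*Combined protocol and SAP*

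**What the plan says.** Under Potential risks, within section 6, the protocol has a single sentence: "No attributed risks can be related to the study".

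The background in section 4 is mixed. It says of the laparoscopic operation that "its safety, reproducibility, and oncological outcomes are still debated due to its technical complexity and prolonged operating time", and that it "is a relatively new procedure which lacks a clear consensus regarding its benefits". It also says that laparoscopy brings its advantages "without increasing the rate of postoperative complications or compromising oncological outcomes". Of pancreaticoduodenectomy as such it says that "it continues to be a morbid operation with complications ranging from 24-59" per cent.

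The Methodology says that "patients will be selected to undergo total laparoscopic pancreaticoduodenectomy or open pancreaticoduodenectomy through a randomized manner". Among the primary outcomes in section 9 is "Assessment of early post-operative complications including: pain, respiratory complications (collapse, pleural effusion or pneumonia"), and pancreatic and biliary leakage is a further one.

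On monitoring, the Methodology plans bedside checks of chest, wound and abdomen, for example "Daily serial abdominal examination to exclude or suspect pancreatic or biliary leakage will be done". The confidentiality paragraph gives the research ethics committee and health authorities a right to review patient data. The available text describes no route by which adverse events reach anyone during the trial.

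**The concern.** A risk statement in a randomised trial should cover what changes for a patient because of taking part. Here, allocation decides which of two major operations is performed. If the approaches differ in harm, some patients bear that difference because they were randomised. A statement that no risk can be attributed to the study is tenable only if the approaches are known to be equally safe. The protocol does not claim to know this, and it sets out to compare them on harms.

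At stake is whether the protocol describes its own risks correctly, and whether serious events are looked at by arm while the trial is running. Section 9 does not name death or reoperation as outcomes, and nothing in the available text forwards them, or leaks, to a reviewing body.

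**Working it through.** The main check compares statements. The arithmetic only shows what the protocol's figures can and cannot say about risk.

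**Statements side by side**

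| Place | What it implies about risk |
|---|---|
| Section 6, Potential risks | None attributable to the study |
| Section 4, on laparoscopy | Safety and oncological results debated; longer operation; no clear consensus on benefit |
| Section 4, same background | Complications not increased by laparoscopy |
| Section 6, Methodology | Randomisation, not clinical choice, fixes the approach |
| Section 9 | Respiratory complications and leakage compared as primary outcomes |

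1. Eligible patients need a pancreaticoduodenectomy and must be fit for either approach (section 6). The risk common to both approaches therefore exists outside the trial.
2. The trial adds random choice of approach. The study-attributable part is the risk under the assigned approach minus the risk under the approach the patient would otherwise have had.
3. Section 4 gives no figure for that difference and describes the matter as open. The entry in section 6 in effect sets it to zero.

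**What the 24–59% range gives**

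Section 10 plans 12 per group, 24 in total. That figure can be reproduced from the hospital-stay inputs:

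- difference 8.9 − 4.7 = 4.2 days;
- pooled SD √((1.125² + 5.425²)/2) = 3.918;
- standardised difference 4.2/3.918 = 1.072;
- a one-sided t-test at 0.05 with 80% power needs 11.50, rounded up to 12. A two-sided test needs 14.68, rounded up to 15. Sidedness is not stated.

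The size was thus set by length of stay, not by harms. It is used here only for scale.

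If the general range applied to all trial patients (an assumption):

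- expected patients with a complication: 24 × 0.24 = 5.8 to 24 × 0.59 = 14.2;
- chance of at least one at the lower rate: 1 − 0.76²⁴ = 0.9986.

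These figures describe the expected event load in both arms together. They do not measure study risk, because step 1 applies to all of it.

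**What the trial could learn about the difference**

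With a common complication rate p and 12 per arm, the approximate 95% half-width for the difference is 1.96 × √(2p(1 − p)/12):

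- p = 0.24: 1.96 × √0.0304 = 0.342;
- p = 0.50: 1.96 × √0.0417 = 0.400;
- p = 0.59: 1.96 × √0.0403 = 0.394.

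Even an observed difference of zero would leave true differences of about 34 to 40 percentage points in either direction compatible with the data. The completed trial could not justify the sentence afterwards.

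**The case against.** The best defence is a narrow reading: the entry means no risk beyond that of two accepted operations, in patients who need one of them anyway. Section 4 lends this some support, since it says that laparoscopy does not raise complications and calls it a feasible alternative in experienced hands. Daily clinical checks are planned, leakage is a primary outcome, and the ethics committee may inspect the data.

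Part of this stands. The background is not uniformly adverse, and nothing in it shows that laparoscopy is more dangerous. But the same background also calls safety debated, and the entry does not state the narrow meaning or list the risks of either approach. Bedside checks detect events in individual patients; they do not put events by arm before anyone.

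A reader might infer three stronger things, which the documents do not support:

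- **That 24–59% is the laparoscopic rate, or the risk added by the study.** It is given for pancreaticoduodenectomy in general.
- **That patients or the ethics committee were misinformed.** The consent pages and front matter are not in the available text, so what either was told cannot be checked.
- **That the sentence is the reason no safety reporting is described.** Nothing in the protocol links the two.

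**Conclusion.** The entry is wrong as written, not merely incomplete. It cannot be reconciled with a background that leaves the safety of one arm open, with random assignment of the approach, and with primary outcomes that compare harms. Any difference in risk between the approaches is a study risk.

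The size and direction of that risk are unknown. The documents give no figure for it, and 12 patients per arm could estimate it only to within about 34 to 40 percentage points, assuming a common complication rate somewhere in the protocol's own range.

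The point does not affect allocation, outcome definitions or analysis. It concerns the accuracy of the risk statement and, separately, the absence of any described reporting of events during the trial. The second part rests on the available text; a procedure on a removed page would answer it.

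**What to change.** Replace the sentence under Potential risks with text that makes four statements, all drawn from the protocol:

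- allocation decides which operation is performed;
- pancreaticoduodenectomy, by either approach, carries a reported complication rate of 24–59%;
- the laparoscopic approach takes longer;
- its safety and oncological results relative to open surgery are not settled.

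Attach the complication range explicitly to both arms so that it is not read as a laparoscopic rate. Reconcile the two statements in section 4 about laparoscopic safety, and check that the consent information agrees with the new text.

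Add a short paragraph providing that deaths, reoperations and leaks are reported by arm to the research ethics committee, which already has a right to review the data. No event count for pausing recruitment is proposed: at the general complication rate, background events alone could reach one.

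The cost is a less favourable risk statement, a wording change in the protocol and possibly in the consent form, and a small amount of reporting work in a trial of 24 patients.

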**9- Study outcomes:**

- **Primary outcome:**

- o Operative time
- o Assessment of early post-operative complications including: pain, respiratory complications (collapse, pleural effusion or pneumonia)
- o Incidence of pancreatic and biliary leakage

- **Secondary outcome:**

- o ICU stay and total hospital stay
- o Patient satisfaction in terms of pain, ambulation, ability to resume daily routine activities
- o Blood loss and need for blood transfusion accordingly

- Wound complications including: infection (early) and incisional hernia/port site hernia (late)
- Pathological assessment in terms of LN harvesting and resection margins (R0 resection or R1)

---

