#### 10- Sample size

The sample size was assessed using the G \* power 3.1.9.4 software (Universities Kiel, Germany). The calculation was based on the study of Ammori et al. [11], which reported a mean hospital stay length of  $4.7 \pm 1.125$  days in the OPD group compared to a respective mean of  $8.9 \pm 5.425$  days in the LPD group. After setting the study power at 80% and  $\alpha$  at 0.05, a minimum of 12 patients in each group were required.

---

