#### 11- Statistical analysis

#### 12- Source of funding:

- No Funding

---

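### Section 9 lists several unranked primary outcomes with no rule for combining them, and the 12 per group has no stated power for any of them

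*Combined protocol and SAP*

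**What the plan says.** Section 9 places three bullets under its primary heading. The first is operative time. The second is "Assessment of early post-operative complications including: pain, respiratory complications (collapse, pleural effusion or pneumonia"). The third is "Incidence of pancreatic and biliary leakage". None is ranked above the others. Counted plainly they contain five measures: operative time, pain, respiratory complications, pancreatic leakage and biliary leakage. It is not said whether the three respiratory events form one outcome, or whether leakage is one outcome or two.

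The Methodology part of Section 6 defines operative time. It also says how the other measures are assessed: a visual analogue scale for pain, daily chest assessment, and daily abdominal examination for leakage with laboratory tests and imaging if needed. It gives no diagnostic thresholds and no time points for analysis.

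Section 10 sizes the trial on hospital stay and concludes that "a minimum of 12 patients in each group were required", with power 80% and alpha 0.05. Section 9 lists "ICU stay and total hospital stay" as secondary. The heading "11- Statistical analysis" has no text beneath it in the available document.

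**The concern.** Section 5 aims to weigh the advantages and disadvantages of the laparoscopic approach and to lower operative morbidity. The plan does not say which primary result would answer that aim, or whether one, some or all of the primary results must favour one approach. Followed as written, it gives several primary tests with no error control, and a stated 80% power that covers none of them.

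Two things are at stake. First, while the rule stays open until results are known, the reading that suits them can be chosen. Second, a reader may take 12 per group as adequate for the morbidity question, when the calculation behind it concerns a different outcome. A non-significant morbidity comparison would then look like evidence of no difference when it says very little.

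**Working it through.** **The plan's own figure.** Inputs from Section 10: means 4.7 and 8.9 days, SDs 1.125 and 5.425, power 80%, alpha 0.05, sidedness not stated.

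- Difference = 8.9 − 4.7 = 4.2 days. Pooled SD = √((1.125² + 5.425²)/2) = 3.918. Standardised difference = 4.2/3.918 = 1.072.
- A one-sided t-test needs 11.5, so 12 per group (power at 12 = 81.6%). This reproduces the stated figure.
- A two-sided t-test needs 15 per group; power at 12 is 70.9%.

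All of these inputs concern hospital stay. None concerns a primary outcome.

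**Error if any one of five primary results counted.** This rule is an assumption, since the plan states none. Further assumptions: two-sided 0.05, independent tests, operative time and pain each tested at exactly 5%, and the three incidences (respiratory complications, pancreatic leakage, biliary leakage) tested by Fisher's exact test at 12 v 12 with event rates of 10-50%.

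- The true size s of one Fisher test is 0.0025 at a 10% rate, 0.0151 at 25% and 0.0228 at 50%.
- Nothing truly differs: 1 − 0.95² × (1 − s)³ = 0.104, 0.138 and 0.158.
- Only operative time differs: 1 − 0.95 × (1 − s)³ = 0.057, 0.092 and 0.114.
- Operative time and pain both differ: 1 − (1 − s)³ = 0.007, 0.045 and 0.067.

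The last case is the one Section 4 points to. It says that safety and oncological outcomes "are still debated due to its technical complexity and prolonged operating time", and credits the laparoscopic approach with "reduced blood loss, decreased postoperative pain, and shorter length of hospital stay".

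**Power for morbidity at 12 per group.** Section 4 says of pancreaticoduodenectomy that "it continues to be a morbid operation with complications ranging from 24-59"%. That range is taken here as the comparator rate and is assumed to be halved. The range comes from the plan; the halving is an assumption. Exact Fisher test, two-sided 0.05:

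- 24% v 12%: 3.5%
- 59% v 29.5%: 20.3%
- 24% v 0%: 13.8%

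The range covers overall complications, so a rarer single complication would have less power for the same relative reduction.

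**What 12 per group can detect.**

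- Continuous primary, two-sided t-test, 80% power: 1.20 SD at 0.05.
- Binary primary, Fisher p-values by number of events out of 12 in each group: 0 v 5, p = 0.037; 1 v 6, p = 0.069; 1 v 7, p = 0.027; 2 v 8, p = 0.036.

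**Holm over five outcomes.** The first threshold is 0.05/5 = 0.01. If two outcomes are rejected first, the next is 0.05/3 = 0.0167. For an assumed 10% v 40%, Fisher power is 23% at 0.05, 12% at 0.0167 and 7% at 0.01. The 7% is the first-step worst case.

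**The case against.** The strongest reply is that this is a small comparative study. Section 5 speaks of advantages and disadvantages and states no formal hypothesis, so the trial need not have one result that makes it positive. Results in opposite directions would be informative, and leakage and respiratory events could reasonably be safety estimates. Several primary outcomes can also be legitimate. All of that is fair. But Section 9 calls these outcomes primary, and Section 10 sets alpha and power as for a test. If the role is descriptive, the plan should say so.

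It can also be said that the Methodology narrows the loosely worded complication list through its planned assessments. It does, in part; thresholds and analysis times are still missing.

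Three stronger readings are tempting, and the documents do not support them:

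- A reader might infer that the false-positive rate is known to be several times 5%. That needs an any-one-counts rule the plan never states and no true difference on any outcome, which is contrary to Section 4's expectation.
- A reader might infer a joint power by assuming 80% for each outcome under a rule that all must succeed. Nothing gives any primary outcome 80%, and the Fisher results above show far less for morbidity.
- A reader might infer that the plan contains no alpha or power at all, or that no analysis section was ever written. Section 10 gives both figures, for hospital stay. The empty Section 11 shows only that the available version has no text there.

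**Conclusion.** The point holds. The plan has about five primary measures, no rule for combining them or controlling error, and no stated power for any of them.

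Error inflation is conditional: about 10-16% if any one of five counts and nothing truly differs, and 0.7-6.7% if operative time and pain truly differ. Both ranges assume independent tests and event rates of 10-50%.

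Low power for morbidity is the more serious consequence: about 3.5% to 20% at 12 per group. This rests on using Section 4's overall complication range as the comparator rate and on an assumed halving. Even removing all complications from a 24% rate would give only 13.8%. The plan should be changed, and the change is mostly wording.

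**What to change.** Before outcome data are seen:

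- **Section 9:** name one primary outcome, with a definition and a time point. Operative time is already defined in the Methodology; a morbidity outcome fits Section 5 better.
- **Section 11:** state the test, alpha and sidedness for that outcome. Label all other outcomes secondary or safety, reported as estimates with 95% confidence intervals. If several stay primary, apply Holm over a fixed, defined list.
- **Section 10:** restate what 12 per group can detect for the named outcome, using the continuous or binary limits shown in the working.
- **Section 5:** if operative time is named, or if morbidity cannot be powered at 12 per group, say that the morbidity comparison is descriptive.

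The cost is fewer confirmatory claims and a less favourable power statement. Keeping morbidity confirmatory would cost much more: about 49 per group to detect 59% v 29.5%, or about 174 for 24% v 12% (Fisher, 80% power, two-sided 0.05). Keeping five primaries under Holm would raise the detectable continuous difference to 1.51 SD at the first step and leave the incidence outcomes with little power.
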